At the start of each in-person study visit, participants will undergo a breathalyzer test to measure breath alcohol concentration (BrAC). For the consent visit, BrAC must be 0.00 before informed consent procedures can be initiated. If the participant has a BrAC greater than 0.00, he/she will either be: (a) sent home and scheduled to return on another day (when BrAC is over 0.03%), or (b) offered something to eat and water to drink, and then re-do the BrAC after sufficient time has passed to determine if it has dropped to 0.00 (when BrAC is in the range of 0.01-0.03%).

For all other study visits, BrAC will be measured at the start of the visit. (1) All participants with BrAC at or below 0.02% will continue with study assessments. If a participant has a BrAC in the range of 0.02% - 0.04%, study staff will determine if the participant can put forth good effort on the study measures. If judged to be so, the participant will continue with study assessments. If judged to not be so, the participant will either be: (a) sent home and scheduled to return on another day (when BrAC is over 0.06%), or (b) offered something to eat and water to drink, and then re-do the BrAC after sufficient time has passed to determine if it has dropped to or below 0.04% (when BrAC = 0.05%). If a participant decides to leave the study site with a BrAC greater than 0.02% rather than wait or complete the study visit, the research team will make a reasonable effort to reach the participant later in the day to ascertain his/her safety and to encourage him/her to attend the next clinic visit.

I. Telephone Screening

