No assessments will be performed at any subsequent visit unless participants have a BrAC of 0.02% or less. If the participant attends the clinic and has a BrAC greater than 0.02%, the study staff will encourage the participant to wait in the clinic for a sufficient time to permit testing. If a participant records a BrAC > legal definition of intoxication, s/he will be advised to wait until the level falls below the legal level. If the participant insists on leaving with a BrAC that is at or above the legal level, this will be documented in the appropriate section of the CRF. The research team will make a reasonable effort to reach the participant after s/he leaves the clinic to ascertain his/her safety and to encourage him/her to attend the next clinic visit.

If following the in-person screening visit it is determined that an individual meets all eligibility criteria, he/she will be randomized to study condition. The IDS Pharmacy holds the randomization schedule. The study team will provide the necessary information to the IDS Pharmacy for randomization. Specifically, Co-Investigator [name] determines the genotype and then provides this information to the pharmacy, along with gender, methadone status (yes/no), and depression/anxiety symptoms (High or low). This procedure ensures that all raters, investigators, and other staff are blind to treatment assignments except for the dispensing pharmacist.

The UM Investigational Drug Service (IDS) will provide medication for all study participants, including those who are recruited at the VAMHCS.

III. Baseline Visit (Visit 1)

Participants who have one of the specific desired genotype combinations will be notified of that fact within approximately one week and asked to return within approximately 30 days from screening for the baseline visit. At the baseline visit, the participant will be informed of the randomization and will receive the first dose of pregabalin or placebo based on their assigned randomization schedule. The baseline visit can be spread out over 2 visits, depending on participants' availability and convenience. The baseline visit will consist of the following:

1. BrAC, vital signs, weight, height – summarized on the Vital Signs Form.
2. Urine collection (summarized on the Urinalysis Form) to:
 - 2a test for pregnancy(for women of child-bearing potential).

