Once it has been determined that the participant meets all inclusion and no exclusion criteria, the study medical provider will administer the first dose of study medication and dispense the first week of medication to the participant, giving instructions on how to take the medication twice daily for 12 weeks. The study staff will instruct the participant to call at any time to discuss any problems or concerns that they may have while taking the study medication.

At the end of this visit, study staff will provide instructions about how to participate in remote visits easily and safely. We will strongly encourage the participant to choose a confidential location for these questionnaires. Participants will also be given assistance with using their mobile device or computer for secure video chat via Zoom for Remote Treatment Visits (see below).

Participants will also be instructed to call the study staff at any time even when participating remotely (and on days that no study visits are scheduled) to discuss problems or concerns that they may have while participating in the study. They will be provided with phone numbers to contact the study staff during office hours and a pager number for off-hours contact.

IV. On-treatment visits (Visits 2-11)

Participation will take place every week (+/- 6 days) for 12 weeks. Visits 3, 5, 6, and 9 will occur in-person at an approved study site (referred to below as "In-Person Treatment Visits"), while Visits 2, 4, 7, 8, 10, and 11 will occur remotely by phone or secure Zoom video chat (referred to below as "Remote Treatment Visits"). At each in-person visit, an appropriate amount and doses of study medication will be dispensed so the participant has enough to last until the next in-person visit. All participants who are randomized will be taught the correct use of the study medication which is reviewed at each study visit.

For Remote Treatment Visits, all self-report measures will be administered by a study staff member.

The following list identifies the measures that will be completed during the treatment phase of the study, and at which visits they will be completed:

1. BrAC, body weight, and vital signs (In-Person Treatment Visits) – summarized on the Vital Signs Form.

2. TLFB (All Visits)

3. PCL (All Visits)

4. CIWA-Ar (All Visits) – items that refer to clinical judgment based on participants' physical appearance/demeanor will be omitted for Remote Treatment Visits

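### The protocol gives two incompatible breath-alcohol rules for in-person visits after consent, and one of them leaves some readings with no action

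*Protocol*

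**What the plan says.** The rule appears twice in the Protocol, under Study Procedures. This point concerns visits after consent, not the limit for the consent visit itself.

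**Opening text, before I. Telephone Screening (all visits other than consent).** "All participants with BrAC at or below 0.02% will continue with study assessments". Next, "If a participant has a BrAC in the range of 0.02% - 0.04%, study staff will determine" whether an adequate effort is possible. "If judged to be so, the participant will continue with study assessments". Participants judged unable have two possible actions. One is to be "sent home and scheduled to return on another day (when BrAC is over 0.06"%. The other, tied to a reading of 0.05%, is food, water and a retest to see whether the reading has come down to 0.04% or lower.

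**Closing text of II. In-person Screening (visits after screening).** "No assessments will be performed at any subsequent visit unless participants have a BrAC of 0.02% or less". Anyone above 0.02% who comes to the clinic is encouraged to stay until testing is possible. Above the legal definition of intoxication, "s/he will be advised to wait until the level falls below the legal level". No figure is given for the legal level. This text has no staff-judgement exception, no 0.04% level and no instruction to send anyone home.

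**Where the rule applies.** Section IV lists the test as "1. BrAC, body weight, and vital signs (In-Person Treatment Visits"), while TLFB and PCL are listed for all visits. Sections IV and V, with the visit list under item 3 of Study Procedures, make Visits 3, 5, 6, 9 and 12 in-person and Visits 2, 4, 7, 8, 10 and 11 remote. Section IV gives a window of +/- 6 days. The TLFB item in section II collects a missed drinking period at the next attended visit. No equivalent provision is given for the PCL or CAPS.

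**The concern.** Neither text refers to the other or says which prevails. A participant at 0.03% is assessed or not, and a participant at 0.07% is sent home or asked to wait, according to which text the staff member follows. For an intoxicated participant, two different instructions are a defect in the safety procedure itself.

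The statistical stake is which outcome data get collected. Anyone stopped under either text has a reading above 0.02%, so any resulting missingness is tied to recent drinking, which is one of the outcomes. The PCL supplies both Aim 2 primary outcomes. The modified plan (SAP Item 3) analyses 44 participants with 40% cumulative attrition and describes no separate handling of missing data. Section II requires a CRF entry only when someone leaves at or above the legal level, so other stopped visits need not be traceable.

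**Working it through.** No sample size, power or alpha figure enters this point, so there is no figure of the plan's to reproduce. The check sets the two rules side by side in 0.01% steps and then counts the visits affected.

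**Step 1. Action at each reading.** The opening text is read generously: its actions at 0.05% and over 0.06% are taken to apply to those readings, although they are written as branches of the 0.02%-0.04% band.

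| Reading | Opening text of Study Procedures | Closing text of section II | Same? |
|---|---|---|---|
| 0.00%, 0.01%, 0.02% | Assess | Assess | Yes |
| 0.03%, 0.04% | Assess if staff judge effort adequate; otherwise no action stated | No assessment; wait until 0.02% or less | No |
| 0.05% | Food, water, retest; resume at 0.04% or less | No assessment; wait until 0.02% or less | No |
| 0.06% | No action stated | No assessment; wait until 0.02% or less | No |
| 0.07% to 0.10% | Send home, return another day | No assessment; wait in clinic, and if above the legal level, until below it | No |

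Of the 11 steps, 3 agree and 8 differ. The conflict over 0.06% does not depend on the legal level, because section II encourages waiting from any reading above 0.02%.

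**Step 2. Gaps inside the opening text.**
- Poor effort at 0.02%-0.04%: the two actions are conditional on readings over 0.06% or equal to 0.05%, so neither applies.
- Exactly 0.06%: neither over 0.06% nor equal to 0.05%, so no action.
- Exactly 0.02%: in both the continue band and the judgement band.

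**Step 3. Visits affected.**
- Post-baseline visits: Visits 2 to 12 = 11.
- In-person: 3, 5, 6, 9, 12 = 5. Remote: 2, 4, 7, 8, 10, 11 = 6. Check: 5 + 6 = 11.
- Exposed share of post-baseline PCLs: 5/11. Counting the baseline visit, which is also in person, it is 6/12.
- On-treatment CAPS: Visits 5, 9 and 12, so 3 of 3 fall at exposed visits.
- %dCDT and GGT draws during treatment: Visits 6 and 12, so 2 of 2 fall at exposed visits, if a blood draw counts as an assessment.

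**Step 4. Effect on the results.** This would need the number of visits stopped for breath alcohol, by arm, and how many were later made up. The documents give neither, so no figure is computed.

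**The case against.** The strongest reply is that the conflict is one of wording and need cost no data. The opening text schedules a return for those sent home and retests those at 0.05%. Section II has people wait so that testing can be done. The window is +/- 6 days, and the TLFB provision largely protects the heavy-drinking outcome for anyone who returns. All of this stands, and it limits the consequence to data at risk. It does not remove the contradiction, since the two rules still cannot both be followed above 0.02%.

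Some stronger readings are tempting but not supported:

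- **Remote assessments are barred.** A reader might infer this from section II's reference to any later visit. The context rules it out: the next sentence speaks of a participant attending the clinic, the opening text concerns in-person visits, and section IV lists the breath test for in-person visits only.
- **The results are biased by some fraction of an SD against pregabalin.** Any such figure needs assumed loss rates by arm and an assumption that nothing is recovered. The direction would come from the assumed difference between arms, and the documents give no basis for it.
- **All laboratory markers are blocked.** Assessment is not defined, and a test of effort does not naturally apply to a blood draw. The %dCDT and GGT exposure is therefore conditional.
- **Intoxicated participants are simply turned out under one rule.** The opening text does not say that they leave at once, and both texts provide for contact with some participants who leave. The instructions differ, but the documents do not show more than that.

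**Conclusion.** The contradiction is certain and needs no outside fact: the two texts cover the same in-person visits after consent and conflict at every tested reading above 0.02%. The opening text is also incomplete on its own terms. Exposure is 5 of 11 post-baseline visits, all three on-treatment CAPS and 5 of 11 post-baseline PCLs. Any assessment missed for this reason would be missing in connection with recent drinking.

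The size of the effect on the trial's results is unknown and cannot be derived from the documents. Aim 1's heavy-drinking outcome is largely protected for participants who return, so the more exposed outcomes are the PCL cluster scores at in-person visits and the CAPS. This should be corrected, but it is not evidence that the results are biased. Which levels are right is a clinical question and is not judged here.

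**What to change.** Reconcile the opening text of Study Procedures and the closing text of section II into one rule for in-person visits after consent. It needs non-overlapping bands that cover every reading, one level at which assessment resumes, and one instruction for readings above the upper band. The sponsor's clinicians should set all the levels.

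State that when an in-person visit is stopped for breath alcohol, the assessments due are rescheduled within the existing +/- 6 day window: PCL and TLFB by the remote procedure already in section IV, CAPS at a return in-person visit. CAPS is scheduled only in person, so doing it by telephone would be a new procedure. Record the reason for every stopped visit, not only for departures at or above the legal level.

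SAP Item 3 says that data collection closed in December 2021, so new wording cannot change what was collected. The report should therefore state which rule was applied in practice and the number of visits stopped for breath alcohol in each arm.

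The cost is protocol wording, one recorded reason per stopped visit and a short tabulation. The small downside is that a rescheduled score falls a few days later than its nominal date.

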3. TLFB
4. PCL
5. PSQI
6. Clinical Institutes Withdrawal Assessment for Alcohol (CIWA-Ar) (Sullivan JT, Sykora K, Schneiderman J, Naranjo CA, Sellers EM. Assessment of alcohol withdrawal: the revised clinical institute withdrawal assessment for alcohol scale (CIWA-Ar). *Br J Addict.* 1989 Nov;84(11):1353-7.) - The CIWA-Ar consists of 10 items, 9 of which (nausea and vomiting, tremor, paroxysmal sweats, anxiety, agitation, tactile disturbances, auditory disturbances, visual disturbances, headache, fullness in head) are rated on a scale of from 0 to 7. The 10th item (orientation and clouding of sensorium) is rated on a scale of from 0-4. It takes approximately 2 minutes to administer and score the CIWA-Ar. The CIWA-Ar scale will be administered by the investigator or another qualified member of the research team. The research team member who administers the CIWA-Ar assessment will be trained in the scoring conventions for the scale.
7. Obsessive Compulsive Drinking Scale (OCDS) (Anton RF, Moak DH, Latham P. The Obsessive Compulsive Drinking Scale: A self-rated instrument for the quantification of thoughts about alcohol and drinking behavior. *Alcohol Clin Exp Res* 1995;19(1):92-99.) - The OCDS is a 14-item, self-administered questionnaire for characterizing and quantifying the obsessive and compulsive cognitive aspects of craving and heavy (alcoholic) drinking, such as drinking-related thoughts, urges to drink, and the ability to resist those thoughts and urges. It has sensitivity as a monitoring tool and has predictive validity for relapse drinking. Preliminary data also indicate that the OCDS may be a useful screening instrument for the presence of AUD, and may be used to differentiate between individuals with AUD and those who do not drink excessively.
8. Patient Health Questionnaire 9 (PHQ 9; Spitzer RL, Kroenke K, Williams JB (1999). Validation and utility of a self-report version of PRIME-MD: the PHQ primary care study. *JAMA.* Nov 10;282(18):1737-44) - The PHQ-9 is The PHQ-9 is a brief self-report tool that is used to screen for symptoms of depression. It incorporates DSM depression diagnostic criteria into 9 items, each of which are scored on a scale of 0 (not at all), 1 (several days), 2 (more than half the days), and 3 (nearly every day). The PHQ-9 will be administered at every study visit. At screening/baseline, participants with severe, untreated depression or who endorse suicidal intent will be excluded from the study and referred for treatment or immediate intervention. At each post-baseline visit, the staff will review the findings on the PHQ-9 to ensure that the participant's safety is not compromised by changes in depression symptoms.
9. Addiction Severity Index - Lite (McLellan AT, Luborsky L, Woody GE, O'Brien CP (1980). An improved diagnostic evaluation instrument for substance abuse patients. The Addiction Severity Index. *Journal of Nervous and Mental Disorders*, 168 (1):26-33.) - The Addiction Severity Index, Lite version (ASI-Lite) is a shortened version of the Addiction Severity Index (ASI). The ASI is a semi-structured instrument used in face-to-face interviews conducted by clinicians, researchers, or trained technicians. The ASI covers the following areas: medical, employment/support, drug and alcohol use, legal, family/social, and psychiatric. The ASI obtains lifetime information about problem behaviors, as well as problems within the previous 30 days. The ASI-Lite contains 22 fewer questions than the ASI and omits items relating to severity ratings, and a family history grid.
10. Short Index of Problems (SIP) (Blanchard K; Morgenstern J; Morgan TJ; Labouvie EW; Bux DA. Assessing consequences of substance use: Psychometric properties of the Inventory of Drug Use Consequences. *Psychol Addict Behav* 2003;17(4):328-331 [though the article title says it is about the DrInC, it is also about the development of the SIP-AD] - The Drinker Inventory of Consequences (DrInC) measures overall consequences of drinking and yields five subscale scores. A short form of the DrInC, the Short Index of Problems (SIP), was developed for use when time does not permit completion of the DrInC. The SIP is a 15-item self-report instrument that measures specific and direct harmful consequences of drinking. Each item is assessed on a 3-point scale ranging from "never or once or a few times" to "daily or almost every day." A lower score indicates fewer adverse consequences of drinking.
11. Clinical Global Impression Scales (CGI-S and CGI-I) (Guy W (ed) (1976) ECDEU assessment manual for psychopharmacology. US Department of Health, Education, and Welfare, Rockville, MD) - The clinical global impression (CGI) rating scales are commonly used clinician-rated measures of global symptom severity and treatment response for patients with mental disorders. Many researchers, while recognizing the validity of the scales, consider them to be subjective as they require the clinician to compare the participants under examination to typical patients from their clinical experience. The Clinical Global Impression – Severity scale (CGI-S) is a seven-point scale that requires the clinician to rate the severity of the patient's illness at the time of assessment, relative to the clinician's past experience with patients who have the same diagnosis. Considering total clinical experience, a patient is assessed on severity of mental illness at the time of rating. Ratings: 1 = Normal, not at all ill, 2 = Borderline mentally ill, 3 = Mildly ill, 4 = Moderately ill, 5 = Markedly ill, 6 = Severely ill, 7 = Extremely ill. The Clinical Global Impression – Improvement scale (CGI-I) is a seven-point scale that requires the clinician to assess how much the patient's illness has improved or worsened relative to a baseline state at the beginning of the intervention. Ratings: 1 = Very much improved, 2 = Much improved, 3 = Minimally improved, 4 = No change, 5 = Minimally worse, 6 = Much worse, 7 = Very much worse.
12. WHO DAS (http://www.who.int/classifications/icf/more_whodas/en/) - A global functioning measure developed by the World Health Organization. It can be used across all diseases, including mental, neurological, and addictive disorders. It is short, simple, and easy to administer (5 to 20 minutes), and applicable in both clinical and general population settings. It covers 6 Domains of Functioning, including: Cognition – understanding & communicating, Mobility– moving & getting around, Self-care– hygiene, dressing, eating & staying alone, Getting along– interacting with other people, Life activities– domestic responsibilities, leisure, work & school, Participation– joining in community activities
13. Quality of Life Enjoyment and Satisfaction Questionnaire (Q-LESQ) (Endicott J, Nee J, Harrison W, Blumenthal R. Quality of Life Enjoyment and Satisfaction Questionnaire: A New Measure. *Psychopharmacology Bulletin* 1993;29:321-326.) - a brief measure of quality of life.

14. Review of medication changes and treatment history since screening – summarized on the Other Medications Review Form.

16. Administration of study medication. Study medication will be started in Visit 1. Participants will start at the FDA-recommended initial dose of 150 mg/day and be titrated over 1-3 weeks to a maximum dose of 450 mg/day taken as one pill twice per day. Participants will be tapered off pregabalin over one week, as recommended in the Lyrica® package insert. Dispensing information is summarized on Pregabalin Dispensing Record.

17. Brief Behavioral Compliance and Engagement Training (BBCET) Session 1 (including the SAFTEE for assessment of adverse events; [name] BA, Ait-Daoud N, Roache JD. The COMBINE SAFTEE: a structured instrument for collecting adverse events adapted for clinical studies in the alcoholism field. *J Stud Alcohol Suppl.* 2005 Jul;(15):157-67; discussion 140. PubMed PMID: 16223067).

If an abnormality is found during the baseline visit that could pose a risk to the participant, prevent the participant from completing study procedures, or interfere with study results, the investigator may decide not to administer study medication.

Once it has been determined that the participant meets all inclusion and no exclusion criteria, the study medical provider will administer the first dose of study medication and dispense the first week of medication to the participant, giving instructions on how to take the medication twice daily for 12 weeks. The study staff will instruct the participant to call at any time to discuss any problems or concerns that they may have while taking the study medication.

At the end of this visit, study staff will provide instructions about how to participate in remote visits easily and safely. We will strongly encourage the participant to choose a confidential location for these questionnaires. Participants will also be given assistance with using their mobile device or computer for secure video chat via Zoom for Remote Treatment Visits (see below).

Participants will also be instructed to call the study staff at any time even when participating remotely (and on days that no study visits are scheduled) to discuss problems or concerns that they may have while participating in the study. They will be provided with phone numbers to contact the study staff during office hours and a pager number for off-hours contact.

IV. On-treatment visits (Visits 2-11)

Participation will take place every week (+/- 6 days) for 12 weeks. Visits 3, 5, 6, and 9 will occur in-person at an approved study site (referred to below as "In-Person Treatment Visits"), while Visits 2, 4, 7, 8, 10, and 11 will occur remotely by phone or secure Zoom video chat (referred to below as "Remote Treatment Visits"). At each in-person visit, an appropriate amount and doses of study medication will be dispensed so the participant has enough to last until the next in-person visit. All participants who are randomized will be taught the correct use of the study medication which is reviewed at each study visit.

For Remote Treatment Visits, all self-report measures will be administered by a study staff member.

The following list identifies the measures that will be completed during the treatment phase of the study, and at which visits they will be completed:

1. BrAC, body weight, and vital signs (In-Person Treatment Visits) – summarized on the Vital Signs Form.

2. TLFB (All Visits)

3. PCL (All Visits)

4. CIWA-Ar (All Visits) – items that refer to clinical judgment based on participants' physical appearance/demeanor will be omitted for Remote Treatment Visits

5. Blood collection (results summarized on the Physical Health and Lab Form):

5a. Blood collection Visits 3 and 9: approximately 11.5 ml (approximately 2 teaspoons) per visit for RNA and miRNA for expression studies (to be stored at -80degreesC for future studies). We will use 0.5-1ml of collected plasma samples to measure plasma/serum pregabalin levels (to perform statistical analyses to test (1) validity of urine pregabalin levels as a surrogate biomarker of plasma/serum levels, and (2) associations with genomic data).

5b. Blood collection Visit 6: approximately 28.5 ml (approximately 6 teaspoons) for gamma-glutamyl transferase (%GGT) and carbohydrate-deficient transferrin (%dCDT) to assess for the validity of self-report of drinking and for RNA and miRNA for expression studies (to be stored at -80degreesC for future studies). We will use 0.5-1ml of this collected plasma sample to measure plasma/serum pregabalin levels (to perform statistical analyses to test (1) validity of urine pregabalin levels as a surrogate biomarker of plasma/serum levels, and (2) associations with genomic data).

6. Urine collection (summarized on the Urinalysis Form) to:

6a. screen for drugs of abuse (Visit 6)

6b. test for pregnancy test (for women of childbearing potential (Visit 6)

6c. test for pregabalin. 15 ml of urine collected to test for pregabalin (as a verification test for pill taking and a surrogate marker of actual concentrations of the drug in plasma/serum to adjust for individual variations) (In-Person Treatment Visits)

7. OCDS (All Visits)

8. PSQI (All Visits)

9. PHQ-9 (All Visits)

10. ASI Lite (Visit 6)

11. SIP (Visit 6)

12. CGI-s and CGI-C (Visit 6)

13. WHO DAS (Visit 6)

14. Q-LESQ (Visit 6)

15. BBCET Sessions (All Visits) (including the SAFTEE for assessment of adverse events)

16. Dispensing study drug (In-Person Treatment Visits)

17. Tracking compliance (In-Person Treatment Visits) - summarized on Pregabalin Dispensing Record

18. Tracking use of other medications (All Visits) – summarized on the Other Medications Review Form.

19. Monitoring of suicidal ideation and behavior (All Visits, as needed) - At all visits, participants will complete the Participant Health Questionnaire 9, a 9-item assessment of depressive symptoms that asks how many days in the last two weeks the respondent experienced different symptoms including thoughts of death and

suicide. A positive response (3+ days or more of suicidal ideation) would lead to the study assessor to engage the participant in a discussion guided by the Suicide Risk Assessment Card to gather more information. If after this discussion the assessor believes the thoughts of suicide are significant, the assessor will contact a health care provider to further evaluate the participant and can utilize a range of other steps depending on the assessment of the senior staff member (provide education on warning signs and when further action would be needed, advise to limit access to means of violence, write a safety plan, call a family member or friend, contact a health care provider). If the participant is deemed a high risk of current suicidal behavior, he/she will be provided with contact for further treatment including (911 and local ER and crisis hotline numbers). If the participant is deemed an imminent risk, the research team will call 911 for transport to St. Agnes Hospital.

For Remote Visits, a different set of procedures will be followed:

1. The study team members will assess the participant further to determine whether intent to harm self and plan to harm self exist.
2. After this assessment, if the study team member's opinion is that the risk of harm is low (no plan, no intent, no means), then he/she will continue with the meeting as planned. At the end of the call, the study team member will advise the participant to talk with his/her outpatient mental health provider soon and will assist as needed in setting up an outpatient appointment.
3. After this assessment, if the staff member's opinion is that there is an elevated risk of harm (maybe plan, maybe intent, maybe means), then he/she will do the following:
 - a. Notify the PI or one of the co-Investigators.
 - b. Work with the participant to contact his/her emergency contact (identified on the Subject Locator Form) and ask this contact to go to the participant's location. The plan can be either that the participant calls the contact or that a study team member makes the call. In either case, the study team member will call the participant back to make sure the plan has been implemented and to problem solve if needed (i.e. identify another person who can come to the participant's location).
 - c. If there is no contact person available and the study staff member believes a threat for self-harm exists, the study staff member will refer the participant to urgent care [i.e. their nearest emergency room] or contact the local crisis response hotline and/or local police (i.e. 911) to evaluate the participant emergently.

20. HAM-D and HAM-A - Visit 6

21. AUDIT - Visit 6

22. CAPS (Visits 5 and 9)

If a participant stops study medication at any time during the study, he/she will be encouraged to continue to attend study visits and participate in all non-study-drug-related procedures.

Emergency unblinding information for each participant will be kept in a locked cabinet at the IDS Pharmacy in the case of a medical emergency. In the event that unblinding is needed, the study physician will call the IDS pharmacy and the pharmacist will inform him of the participant's condition.

V. End of Treatment visit (Visit 12)

1. BrAC, body weight, and vital signs – summarized on the Vital Signs Form.

